		Clinical Study Protocol		
Modified:	24Jun2024		Author:	[name]
Version:	1.0		Approvers:	[name]/[name]
Status:	Final		Page:	7 of 29

The Amara View mask, although already cleared for marketing by the US FDA, is undergoing considerations for design changes. A new competitor minimal contact full-face mask (ResMed AirFit F40) has been recently cleared for marketing by the US FDA and released to the market. Prior to making design updates, this study will evaluate patient preference of the Amara View mask compared to the AirFit F40 to provide feedback to the design team.

Description of the Intervention Studied

Investigational Products

There are no investigational products in this benchmark clinical study.

Products Cleared for Marketing by the US FDA

- Amara View Minimal Contact Full Face Mask (MCFFM)

The Amara View Full-Face Mask is a minimal contact full face mask manufactured by Philips Respironics (Murrysville, PA) that covers the mouth and seals under the nose compared to traditional full-face masks which seal over the nose. The Amara View mask is intended to reduce discomfort on the bridge of the nose. There is no forehead arm, offering patients an enhanced design to keep the field of vision clear. The mask consists of a cushion assembly with three cushion sizes, and a modular frame assembly connected to an entrainment elbow and headgear with two size options. The silicone cushion seals under the nose and around the outer perimeter of the patient's mouth and contains a cutout that allows the nostrils to inhale and exhale through when the mask is under pressure. The cushion assembly can be removed from the frame assembly for cleaning or for replacement of the cushion assembly. This allows for one frame size to attach to all three cushion sizes. A quick release tube with a built-in swivel provides a means for connecting the mask to the breathing circuit. The mask can be secured to the patient via headgear, which attaches to the frame with either magnetic clips or non-magnetic talon clips. Amara View uses a traditional tube in front of the mask with a pig tail tube.

The Amara View MCFFM is for single-patient use in the home or multi-patient use in the hospital/institutional environment. The mask is intended to be used on patients (>66lbs/30kg) for whom CPAP or bi-level therapy has been prescribed.

- AirFit F40 Minimal Contact Full Face Mask

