Adverse event (AE) means any untoward medical occurrence associated with the use of an intervention in humans, whether or not considered intervention related. An AE or suspected adverse reaction is considered “serious” if, in the view of either the investigator or sponsor, it results in any of the following outcomes: death, a life-threatening adverse event, inpatient hospitalization or prolongation of existing hospitalization, a persistent or significant incapacity or substantial disruption of the ability to conduct normal life functions, or a congenital anomaly/birth defect. Important medical events that may not result in death, be life-threatening, or require hospitalization may be considered serious when, based upon appropriate medical judgment, they may jeopardize the subject and may require medical or surgical intervention to prevent one of the outcomes listed in this definition.

An Unanticipated Adverse Device Event (UADE) is any serious adverse effect on health or safety or any life-threatening problem or death caused by, or associated with, a device, if that effect, problem, or death was not previously identified in nature, severity, or degree of incidence in the investigational plan or application (including a supplementary plan or application), or any other unanticipated serious problem associated with a device that relates to the rights, safety, or welfare of subjects. Other important medical events which may not result in any of the outcomes above, but which may require intervention to prevent one of the outcomes above, may in the opinion of the investigator, be considered a UADE.

Adverse Event Classification and Reporting

The severity of all AEs will be assessed by the PI or designee as mild, moderate, or severe using the following guidelines:

- Mild – Events require minimal or no treatment and do not interfere with the subject's daily activities.
- Moderate – Events result in a low level of inconvenience or concern with therapeutic measures. Moderate events may cause some interference with functioning.
- Severe – Events interrupt a subject's usual daily activity and may require systemic drug therapy or other treatment. Severe events are usually potentially life-threatening or incapacitating. Of note, the term “severe” does not necessarily equate to “serious”.)

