PI or designee will record all reportable events with start dates occurring any time after informed consent is obtained until the last day of study participation. At each study visit, the investigator will inquire about the occurrence of AE/SAEs since the last visit.

If an SAE or UADE occurs, the PI or designee shall complete a Serious Adverse Event or Unanticipated Adverse Device Effect Report and submit to the study sponsor for review as soon as possible (e.g., within 24 hours of awareness) and no later than 3 calendar days after site's awareness of event. As the site gains more information (i.e., admission records, hospital discharge summaries) a new report with the new information should be submitted to the Sponsor. The study sponsor is responsible for conducting an evaluation of the SAE or UADE and shall report the results of such evaluation to the reviewing IRB and other agencies as applicable.

Device Deficiencies

A device deficiency refers to the inadequacy in the identity, quality, durability, reliability, safety, or performance of an investigational device, including malfunction, use errors or inadequacy in information supplied by the manufacturer. All device deficiencies will be documented on the device deficiency tracking form. If the device deficiency led to a UADE, the SAE or UADE Report should be completed as noted above.

If a device deficiency had the potential to lead to a UADE but did not result in one, it should be documented on the device deficiency tracking form and submitted to the study sponsor for review

Document ID:	N/A	Document title:	Classification:	For internal use
		Clinical Study Protocol		
Modified:	24Jun2024		Author:	[name]
Version:	1.0		Approvers:	[name]/[name]
Status:	Final		Page:	20 of 29

as soon as possible (e.g., within 24 hours of awareness) and no later than 3 calendar days after site personnel's awareness of event.

Statistical Methods

Determination of Sample Size

This study is not statistically powered. The sample size of approximately 30 trial completers is considered sufficient to gauge directional trends comparing the two mask designs.

General Considerations

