Careful mask application, sizing, and adjustment should address or correct mask-related issues. Participants should be instructed to avoid overtightening the headgear and to only use the mask when the device is on and blowing air to avoid rebreathing exhaled air and potential suffocation. Note that some rebreathing may occur at low pressures. Breathing discomfort should be transient or can be addressed with counseling. However, all of these complications are normally encountered while using PAP therapies, and there should be no additional risk from participating in this study given that participants will be recruited on the basis of being established on therapy.

If a participant reports they have experienced an adverse event, they will be directed to contact the site study staff and instructed to discontinue therapy if appropriate.

Participation Risk:

- The loss of confidentiality is a potential risk of being in the study, but the site and sponsor will do everything to make sure that participant information is protected.
- Participants may experience frustration, fatigue, and anxiety while completing the study activities.

There may be a possibility of unanticipated or unknown risks; however, for this activity Philips has determined that this risk is low.

Publication and Registration

This study will be registered on ClinicalTrials.gov. There may be plans to publish the results of this trial, beyond the use of the data in marketing materials.

Document ID:	N/A	Document title:	Classification:	For internal use
		Clinical Study Protocol		
Modified:	24Jun2024		Author:	[name]
Version:	1.0		Approvers:	[name]/[name]
Status:	Final		Page:	26 of 29

References

2. Adult Obstructive Sleep Apnea Task Force of the American Academy of Sleep Medicine. Clinical Guideline for the Evaluation, Management and Long-term Care of Obstructive Sleep Apnea in Adults. *Journal of Clinical Sleep Medicine*. 2009;05(03):263-276. doi:10.5664/jcsm.27497

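### A near-miss device fault must reach the sponsor within 3 days only if the serious effect it could have caused was unanticipated

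*Combined protocol and SAP*

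**What the plan says.** All references are to the combined protocol and SAP.

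- **Device Deficiencies, general rule.** "All device deficiencies will be documented on the device deficiency tracking form". No time limit and no submission step is attached to this sentence.
- **Device Deficiencies, near misses.** A faster route opens in one case: "If a device deficiency had the potential to lead to a UADE but did not result in one". The form then goes to the sponsor as soon as possible and "no later than 3 calendar days after site personnel's awareness of event".
- **Safety Monitoring.** A UADE is a serious effect, life-threatening problem or death linked to a device that "was not previously identified in nature, severity, or degree of incidence in the investigational plan or application". The definition adds other unanticipated serious problems associated with a device. It also lets the investigator class certain other important medical events as UADEs.
- **Anticipated Adverse Device Effects.** After the bulleted risks, the text says that participants should wear the mask only while the device is running, "to avoid rebreathing exhaled air and potential suffocation". It adds that some rebreathing can happen at low pressure.
- **Adverse Event Classification and Reporting.** An SAE or a UADE that occurs goes to the sponsor within the same 3 calendar days.
- **Scope.** A device deficiency is defined as an "inadequacy in the identity, quality, durability, reliability, safety, or performance of an investigational device". Under Investigational Products the protocol states: "There are no investigational products in this benchmark clinical study".

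**The concern.** A near miss is a fault that could have caused serious harm but did not. Reporting it early allows the sponsor to act while other participants are still using the same mask. Whether the possible harm was foreseen should not decide how fast the report travels.

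The rule as written makes it decide. By tying the deadline to the UADE definition, it takes in the unforeseen hazard and leaves out the foreseen one. The more clearly the protocol has named a hazard, the weaker the duty to report a near miss involving it. The rule for events that have actually happened, which comes just before this section, does not work that way, because it names SAEs as well as UADEs.

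At stake is how promptly the sponsor learns of a faulty mask component. Sample size, endpoints and analysis are not involved.

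**Working it through.** The protocol gives no derived figure to reproduce, so the check sets the rules side by side.

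**Step 1. Trace each kind of deficiency to its deadline.**

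| Situation | Route in the protocol | Deadline to sponsor |
|---|---|---|
| (a) Fault led to a UADE | SAE or UADE report | 3 calendar days |
| (b) Fault led to a serious effect already identified in the plan | SAE report | 3 calendar days |
| (c) Fault could have led to a UADE but did not | Tracking form, then submission | 3 calendar days |
| (d) Fault could have led to a serious effect already identified in the plan but did not | Tracking form | None stated |

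Rows (a) and (b) have the same deadline, so for actual events it makes no difference whether the effect was anticipated. Rows (c) and (d) differ on that point alone.

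**Step 2. Ask whether row (d) can be occupied.** It can if the plan has already identified an effect that could be serious. Rebreathing and potential suffocation both appear under the heading Anticipated Adverse Device Effects. A site that reads that heading together with the UADE definition can reasonably class a fault bearing on either one as a potential anticipated effect. It would then have met the written rule once the form was filled in.

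**Step 3. Ask whether another route supplies a deadline.**

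- *Critical-to-quality review (Assessment of Safety).* This uses survey reports of breathing issues, is done after each interval, and triggers at 20% for any breathing issue or 10% for the listed ones. The denominator is not stated. The two candidates are the roughly 40 to be enrolled and the roughly 30 expected to complete (Number of Subjects).
  - With 40: one report is 1/40 = 2.5%; the triggers need 0.10 × 40 = 4 and 0.20 × 40 = 8 reports.
  - With 30: one report is 1/30 = 3.3%; the triggers need 0.10 × 30 = 3 and 0.20 × 30 = 6 reports.
  - On either count a single report falls short, and a fault without symptoms produces no report.
- *Electronic data capture.* The sponsor has access to it, and adverse events, unscheduled calls and sizing changes are recorded. No time limit is given for a deficiency that caused no event.
- *Monitoring.* This is onsite, remote or both, with details left to a separate monitoring plan. The protocol gives no timing for reviewing deficiency forms.

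These routes may bring a fault to the sponsor's notice. None carries a deadline for a single symptom-free fault.

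**Step 4. Check the scope wording.** Device Deficiencies refers to an investigational device, Investigational Products says there is none, and Assessment of Safety says that both masks are cleared for marketing. These statements must be reconciled.

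**The case against.** The strongest reply is that a site could still put a failed vent or elbow on the 3-day route. Suffocation and rebreathing are mentioned only in connection with use while the device is off and with low pressure. Neither sentence describes a component failing during therapy. The plan gives no severity or incidence for either hazard, so a worse or more frequent case could count as not previously identified. The UADE definition also has a catch-all for other unanticipated serious problems, and it leaves some room for investigator judgment. All of this stands. It means that the right statement is that such near misses are not *required* to be expedited, and not that they never will be. It does not remove the point, because the outcome then depends on how each site reads a definition, and the discretionary sentence concerns events, not near misses.

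It is also fair to say that the study is small, enrols established PAP users and compares two cleared masks, and that no delay or harm has been shown. That limits the weight of the point.

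A reader might infer several stronger claims that the documents do not support:

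- *That the 3-day route is the sponsor's only means of learning of a fault.* Data capture, monitoring and the critical-to-quality review also exist.
- *That the protocol itself regards these hazards as serious.* It does not say so, and describes the overall risk as minimal.
- *That neither mask can have a device deficiency, because neither is investigational.* The section would then have no subject. It is plainly meant for the study masks, and the wording is a leftover inconsistency.
- *That the gap would affect the Post Market Clinical Follow-up activity.* The Study Objectives section sends only secondary-objective data there, namely residual AHI, leak, pressure and adherence.

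**Conclusion.** The point holds for near misses only. A deficiency that could have led to a serious effect already identified in the plan has no stated deadline for submission to the sponsor. The same effect, had it occurred, would be reported within 3 calendar days.

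In size, this is one of the four situations traced, and the consequence is an open-ended interval in place of at most 3 calendar days. How often it would arise is not documented, so no expected count can be given.

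The conclusion rests on two assumptions: that a site could treat rebreathing or suffocation as already identified because the protocol names them under an anticipated-effects heading, and that a fault bearing on either could in some cases have a serious outcome. Both are reasonable readings, but the protocol states neither outright.

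This is a worthwhile, inexpensive improvement to safety oversight. The investigational-device wording is a minor inconsistency to tidy at the same time.

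**What to change.** In Device Deficiencies:

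1. Change the near-miss trigger from a potential UADE to the potential to lead to *an SAE or a UADE*, whether or not the protocol lists the hazard. Keep the existing limit of 3 calendar days. This matches the near-miss rule to the one already used for events that occur.
2. As a minor reconciliation with Investigational Products, define a deficiency by reference to *either study mask* in place of an investigational device.

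The sentence on deficiencies that did lead to a UADE needs no change for this purpose, because any resulting SAE is already reportable on the same timetable.

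The cost is a wording change to two sentences and a few more deficiency forms sent promptly. Visits, data collection from participants, endpoints and analyses are unchanged.

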		Clinical Study Protocol		
Modified:	24Jun2024		Author:	[name]
Version:	1.0		Approvers:	[name]/[name]
Status:	Final		Page:	9 of 29

		
Proportion of patients who prefer the Amara View compared to the AirFit F40 for the following:
 
 • Seal • Comfort • Stability • Noise level • Headgear • Mask cushion attachment ease of use • Less disruptive air venting • Overall preference
Secondary Objective: compare residual AHI values between the Amara View and AirFit F40 masks during PAP therapy.	Residual AHI values will tend not to differ between the Amara View and AirFit F40 masks.	Residual AHI recorded by the participants PAP device while using the Amara View and AirFit F40 masks
Secondary Objective: compare the recorded leak values between the Amara View and ResMed AirFit F40 masks during PAP therapy.	Leak values will tend to be lower for the Amara View mask compared to the AirFit F40 masks.	Leak recorded by the participants PAP device while using the Amara View and AirFit F40 masks.
Secondary Objective: compare the air pressure used during PAP therapy between the Amara View and AirFit F40 masks	Air pressure values will tend not to differ between the Amara View and AirFit F40 masks	Air pressure (cmH20) used during PAP therapy recorded by the participants' PAP device while using the Amara View and AirFit F40 masks
Secondary Objective: compare the adherence to PAP therapy while using the Amara View and AirFit F40 masks	Adherence to PAP will tend not to differ when using the Amara View mask compared to the AirFit F40 mask	Daily hours of use of PAP therapy recorded by the participants' PAP device while using the Amara View and AirFit F40 masks

Data obtained as part of the secondary objectives from this protocol will be used as part of a Post Market Clinical Follow-up Activity.

Document ID:	N/A	Document title:	Classification:	For internal use
		Clinical Study Protocol		
Modified:	24Jun2024		Author:	[name]
Version:	1.0		Approvers:	[name]/[name]
Status:	Final		Page:	10 of 29

Study Design

This is an open-label, randomized cross over trial, comparing patient feedback between the Amara View MCFFM and the AirFit F40 MCFFM. This study will recruit approximately 40 adult patients who are established on PAP or Bi-Level therapy at the time of enrollment.

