Adults who are currently adherent to PAP or Bi-Level therapy will be recruited through sleep clinics. Willing and eligible participants will undertake baseline data collection before using either the Amara View or AirFit F40 masks. Therapy will be delivered using their clinically prescribed PAP or Bi-Level device with no modification to settings.

The study will be completed according to applicable Good Clinical Practices and the Declaration of Helsinki. The study will be monitored onsite and/or remotely, as described below.

Randomization

The order in which participants will use the two masks will be randomized. A fixed allocation permuted-block randomization strategy will be used. Randomization will be administered through the electronic data capture system.

Blinding

There will be no blinding in this trial.

Study Procedures

Recruitment

Participants will be recruited via sleep clinics contracted to recruit participants within the United States. Recruitment may involve a combination of in-person recruitment during clinical appointments, phone calls, and emails. Study staff will be responsible for assessment of inclusion and exclusion criteria (listed below).

Scheduling will be conducted by the site. Participants who are willing to enroll will be scheduled for an in-person visit to provide informed consent and complete study procedures.

Baseline Visit (Visit 1)

Consent, Eligibility and Baseline Information

During the baseline visit, the study site coordinator will review the Informed Consent Form (ICF) with the participant explaining the details of the study and answering any questions the participant may have about the study. If the participant is willing to take part in the study, the ICF will be signed and dated by the participant and the site study representative obtaining consent. A copy of each participant's signed ICF will be given to them for their records.

Those who provide consent will then complete the Demographics Questionnaire (see Appendix I), which collects information about age, gender, sex, race, and ethnicity. Next, they will complete the Baseline Survey (see Appendix II) to collect information about the make and model of their prescribed mask and PAP device. The participants will then complete the Eligibility Questionnaire (see Appendix III) to confirm entry criteria.

Document ID:	N/A	Document title:	Classification:	For internal use
		Clinical Study Protocol		
Modified:	24Jun2024		Author:	[name]

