After the first 15-day trial period with the first study mask, participants will return to the site for their second study visit. Participants will be instructed to bring their PAP device and return the first study mask to the visit.

Participants will complete a mask attributes survey on the first study mask and then they will be fitted with the second study mask. Fitting procedures will follow the same procedure as described above in the baseline visit. After the mask fitting, participants will be given the second study mask to take home and provided with the Instructions for Use. They will be encouraged to use the mask for the full 15 days of the second trial period. Participants will be instructed to contact the site if they have issues with the recommended cushion and/or headgear size as needed.

If participants did not return the first study mask at the second study visit, they will be asked to bring it to the third study visit.

Document ID:	N/A	Document title:	Classification:	For internal use
		Clinical Study Protocol		
Modified:	24Jun2024		Author:	[name]
Version:	1.0		Approvers:	[name]/[name]
Status:	Final		Page:	12 of 29

It is anticipated the survey completion and mask fitting will take approximately 60 minutes to complete.

Visit 3

After the second 15-day trial period with the second study mask, participants will return to the site for the third and final study visit. During this visit, participants will complete a mask-attributes survey on the second study mask and return all study product.

It is anticipated the survey completion and study product return will take approximately 30 minutes to complete.

After participants have completed both study arms, deidentified data from participants' PAP devices will be extracted from the connected device software Care Orchestrator (CO) for Philips device users only. The site coordinator will confirm the data has been uploaded into CO at visits 2 and 3.

Unscheduled Phone Calls

Documentation of unscheduled phone calls will be captured within the EDC.

Conclusion of Participation

Once the participant returns the study mask(s) and completes the survey, their participation in the study will be complete. Participants will be active in the study for approximately 30 days but no more than 60 days after receipt of the first study mask.

Participant Reimbursement

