Modified:	24Jun2024		Author:	[name]
Version:	1.0		Approvers:	[name]/[name]
Status:	Final		Page:	14 of 29

Selection and Withdrawal of Participants

Number of Subjects

Approximately 40 participants will be enrolled. It is anticipated that approximately 30 participants will complete all study procedures.

Recruitment considerations

As indicated below, eligibility is based on participants being established PAP users, and currently not using a Philips Amara View or ResMed AirFit F40 full face mask. Eligibility criteria will be collected via self-report by the participant.

Inclusion Criteria

- Aged 21-85 years (inclusive)
- Weight >66 pounds/30 kg
- Established on PAP for \geq 90 days at the time of consent
- Currently prescribed and using fixed pressure, Auto CPAP, or Bi-Level therapy on a regular basis (average PAP usage of \geq 4 hours/night, \geq 4 days per week for \geq 3 months)
- Currently using a Full-Face mask
- Able to read, write, speak and understand English
- Willing and able to provide informed consent
- Willing and able to follow instructions and complete all activities required by the study
- Able to remove a sleep apnea mask without assistance

Exclusion Criteria

- Currently using a Philips Resironics Amara View FFM or ResMed AirFit F40 FFM
- Allergy to silicone
- Allergy to latex
- Unique facial features (i.e., deformities of the face and/or head, piercings, etc.) that could interfere with the therapeutic use of this type of mask
- Employee or living with a family member who works for Philips or any company that designs, sells, or manufactures sleep-related products.
- Prescribed oxygen at night or continuously
- Recent eye surgery or dry eyes
- Hiatal hernia
- Excessive reflux
- Impaired cough reflux

Document ID:	N/A	Document title:	Classification:	For internal use
Modified:	24Jun2024	Clinical Study Protocol	Author:	[name]
Version:	1.0		Approvers:	[name]/[name]
Status:	Final		Page:	15 of 29

- Impaired cardiac sphincter function
- Using prescription drugs that induce vomiting
- Currently participating in another interventional research study or planned participation in another interventional clinical research study during the trial period
- Prescribed an ASV (adaptive servo-ventilation) device
- Prescribed mechanical ventilation
- Pre-existing conditions such as bullous lung disease, pathologically low blood pressure, bypassed upper airway, pneumothorax, pneumocephalus, cerebral spinal fluid (CSF) leaks, or cribriform plate abnormalities

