All variables will be summarized by descriptive statistics. The statistics for continuous variables will include mean, median, standard deviation, minimum, maximum, 95% confidence interval (CI) for the mean, and number of observations. For categorical variables, frequencies and percentages will be presented. All formal analyses will be conducted using SAS®, and statistical comparisons will be considered significant at an alpha of 0.05, with adjustments for multiple comparisons, as applicable. There are no statistical criteria for terminating the study, and any deviations from the original statistical plan will be noted in the analysis report.

Participant Disposition

Participant disposition, including the total number of participants enrolled, randomized, completed and early terminations, will be presented. In addition, a listing will be provided with the reasons for early termination.

Statistical Analyses

Mask attribute ratings, scaled 0-10, will be collected on both the AirFit F40 and the Amara View Full Face masks. Since the study is not statistically powered, the analysis will focus on the effect sizes and confidence intervals of the paired differences between the masks [Amara View – AirFit F40]. The paired t-test and nonparametric Wilcoxon Signed-Ranks test will further evaluate the trends. In cases where one test calculates a p-value below 0.05 and the other indicates a p-value ≥ 0.05 , the distributions of the paired differences will be inspected to determine which method better models the data. Participants will be excluded from the analysis of a given endpoint if they do not contribute a rating for both study masks.

Residual AHI, leak, air pressure, and average adherence will be extracted from the patients' PAP device data, and the paired differences [Amara View – AirFit F40] will be evaluated as described above.

Percentages and exact binomial confidence intervals will be calculated for categorical questions. The McNemar test will compare binary responses where the same questions are answered after the participants try both masks.

Net Promoter Scores (NPS) will be calculated for the question "Would you recommend this (Amara View FFM or AirFit F40) mask to others?" where the percentage of detractors (ratings 0-6) is subtracted from the percentage promoters (ratings of 9 or 10). Ratings of 7-8 will be considered neutral. Relative NPS will be calculated as [Amara View NPS] – [AirFit F40 NPS].

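### The randomized two-period crossover is analysed by pooled paired differences with no period or sequence term: valid on average under random loss, but less precise near balance unless any period effect on ratings is small

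*Combined protocol and SAP*

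**What the plan says.** The protocol's Study Design section states: "This is an open-label, randomized cross over trial". Under Randomization: "The order in which participants will use the two masks will be randomized", and "A fixed allocation permuted-block randomization strategy will be used". The allocation ratio is not given.

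The two ratings are collected at different points of experience. At Visit 2, "Participants will complete a mask attributes survey on the first study mask and then they will be fitted with the second study mask". At Visit 3, "participants will complete a mask-attributes survey on the second study mask and return all study product". Both appended mask surveys list preference, but only the Day 30 survey lists comparisons between the masks.

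Under Statistical Analyses, the focus is on effect sizes and confidence intervals of the within-participant difference, Amara View minus AirFit F40. Then: "The paired t-test and nonparametric Wilcoxon Signed-Ranks test will further evaluate the trends". Device-recorded endpoints follow the same method, and binary items use McNemar. Only participants with data on both masks are analysed. The optional regressions under Exploratory Analyses concern baseline factors and need not be reported.

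On size, Number of Subjects plans about 40 enrolled, and "It is anticipated that approximately 30 participants will complete all study procedures". Determination of Sample Size says the study is not powered and adds: "The sample size of approximately 30 trial completers is considered sufficient to gauge directional trends comparing the two mask designs".

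**The concern.** A two-period crossover is usually analysed so that any general difference between the periods is separated from the treatment difference. Here the second rating is given after use of both masks and the first after use of only one, in an open-label setting. A period effect on ratings is therefore possible. Its size is not documented, and enrolling established full-face-mask users limits general learning effects.

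If such an effect exists, pooling the two orders does two things. It counts the period effect as noise, which widens the interval that the plan makes its focus. It also lets an unequal number of completers per order move the estimate. Disposition is not reported by order either, so a reader of the results could not see the imbalance.

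**Working it through.** **Plan's own figure.** There is none to reproduce: the plan gives no power, effect size or SD.

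**Inputs from the documents.** N = 30 completers of about 40 enrolled; alpha 0.05 (two-sided assumed); ratings on a 0-10 scale.

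**Assumed inputs.** 1:1 allocation (20/20); loss unrelated to order; SD of the paired difference within a sequence 1.5 to 3, with 2 as the main case; P = 0 to 1 point.

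**Model.** With true mask difference tau, the mean paired difference is tau - P in participants who use Amara View first and tau + P in those who use AirFit F40 first.

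- Planned half-width: t(.975, 29) x sqrt{[SD² + 4P² n1 n2 / (N(N-1))] / N}
- Order-adjusted half-width: t(.975, 28) x SD x 0.5 x sqrt(1/n1 + 1/n2)
- Shift of the planned estimate: P x (n1-n2)/N in absolute size; the adjusted estimate has none

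**Worked case: SD 2, 15/15, P = 1.** The added variance is 4 x 225/870 = 1.034. Planned: 2.045 x sqrt(5.034/30) = 0.838. Adjusted: 2.048 x sqrt(2/15) = 0.748. The planned interval is 12.0% wider.

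**Planned relative to adjusted half-width, SD 2.** The probability of each split is hypergeometric (30 drawn from 20/20).

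| Split | Probability | P=0 | P=0.25 | P=0.5 | P=1 | Shift at P=1 (points) |
|---|---|---|---|---|---|---|
| 15/15 | 0.284 | -0.2% | +0.6% | +3.0% | +12.0% | 0 |
| 16/14 | 0.443 | -0.4% | +0.4% | +2.8% | +11.7% | 0.07 |
| 17/13 | 0.209 | -1.0% | -0.3% | +2.0% | +10.8% | 0.13 |
| 18/12 | 0.056 | -2.2% | -1.4% | +0.8% | +9.3% | 0.20 |
| 20/10 | 0.0004 | -5.9% | -5.2% | -3.2% | +4.4% | 0.33 |

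The 19/11 split (probability 0.008) is not shown but enters the averages. The value of P above which the planned interval is the wider one is 0.11, 0.17, 0.29, 0.43 and 0.75 for the five splits shown.

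**Averaged over random loss, planned relative to adjusted, at P = 0.25 / 0.5 / 1:**

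- SD 1.5: +0.8% / +4.9% / +19.9%
- SD 2: +0.2% / +2.5% / +11.4%
- SD 3: -0.2% / +0.8% / +4.9%

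**Simulation, SD 2, averaged the same way, at P = 0.25 / 0.5 / 1:**

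- Type I error of the planned test: 4.8% / 4.5% / 3.4%
- Power for a 1-point difference, planned: 74.9% / 73.2% / 66.8%
- Power for a 1-point difference, adjusted: 74.9% / 74.9% / 74.8%

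**Preference items.** If being tried second added 10 or 20 percentage points (assumed), the pooled percentage would shift by d x (n1-n2)/N. That is 0.7 or 1.3 points at 16/14, and 2 or 4 points at 18/12.

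**The case against.** The strongest reply has four parts.

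1. **P is wholly assumed.** Rating the second mask after using both is a contrast effect. If it pushes the better mask up and the worse one down equally in either order, the paired difference has the same mean in both sequences and P = 0. This stands: the documents make a uniform shift possible and do not show one.
2. **The loss is small unless P is large.** At P = 0.5 and SD 2 it averages 2.5% of width and under two points of power. At unbalanced splits the planned estimate has the lower root mean squared error until P exceeds SD x sqrt(N)/(2 sqrt(n1 n2)), which is 0.37 at 17/13 and 0.39 at 20/10 for SD 2. This stands too.
3. **Randomized order makes the simple paired analysis legitimate, and the study is descriptive feedback for a design team.** This lowers the priority. It does not remove the point, because the plan chose effect sizes and intervals as its focus for that very reason.
4. **Adjustment is not free for sparse endpoints.** Device data come from Philips users only, and bed-partner items may have few respondents. With no period effect, adjustment widens the interval by about 7% at 10/5 and 11% at 7/3. This stands and limits the scope of the fix.

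A reader might also infer that the planned comparison is biased, since about 10 of 40 are expected not to complete and an inadequate mask is a permitted reason for withdrawal. The documents do not support this. Loss on either mask in either period removes the pair, so mask-related loss alone leaves the sequences balanced in expectation. Systematic bias would need loss that depends on mask and period together. A split such as 20/10 with P = 1 would raise the type I error to about 10%, but under random loss it has probability 0.0004; 18/12 or worse has probability 0.065.

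**Conclusion.** The omission is real, and its consequence is conditional. Under random loss the planned analysis is valid on average: its test is slightly conservative when P is not zero, and the shift averages to zero. What it gives up is precision near balance, by an amount that is negligible at P = 0.25 and worth having at P = 1 (about 5% to 20% of interval width for SD 3 down to 1.5). These figures rest on assumed P, SD, 1:1 allocation and random loss.

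The calculations concern mask ratings, with a side calculation for preference items. They support no claim about the device-recorded endpoints, and the net promoter score difference was not examined. This is a low-priority improvement, worth making because the sequence is already recorded and the cost at about 30 completers is very small.

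**What to change.** In Statistical Analyses:

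1. Report completers, and rating and preference results, by sequence.
2. For the 0-10 mask ratings, make the main estimate and 95% interval the equally weighted mean of the two within-sequence mean differences (for complete pairs, the model with mask, period, sequence and a random participant). Let its t-test replace the paired t-test.
3. Keep the signed-rank and McNemar tests as unadjusted supporting analyses. Apply the rule for disagreement between the t and rank tests only to tests on the same footing. That means either the unadjusted paired t with the signed-rank test, or the adjusted t with a rank test that accounts for sequence. Otherwise an order effect could be read as a distribution problem.
4. State that the change applies to ratings. Device endpoints and items with few respondents keep the planned paired analysis, with a by-sequence summary.
5. State that this adjusts for period only and does not remove carryover or contrast effects.

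**Cost.** SAP wording, a few lines of SAS and one degree of freedom; no new data. With no period effect, the rating interval is 0.2% wider at 15/15, about 2% at 18/12 and 6% at 20/10. The larger cost in small samples is the reason for item 4.
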